6.1.3 Placebo for Alfuzosin

Sanofi-Synthelabo will also be providing the placebo tablets for this trial and shipping them directly to the University of Pennsylvania Investigational Drug Service (IDS) for blinded repackaging and labeling. The placebo tablets will be packaged and labeled identical to the alfuzosin tablets.

6.2 Concomitant Medications

If patients are receiving drugs that cause vasodilation or hypotension (i.e., antihypertensives, nitrates, etc), additive effect may occur during the treatment with the study medication, which could cause dizziness, and even syncope (i.e., related to hypotension). The patients should be warned of the possible occurrence of such events. The investigator will advise the patient of the possibility of postural hypotension during changing position (which should be done gradually during the first few days of treatment); in case of any events of this type, the patients will be instructed to report them to the investigator immediately. The investigator will decide if any action is necessary i.e. whether to allow the patient to continue the trial or to discontinue the trial treatment.

6.2.1 Exclusionary Medications

Participants will be monitored at each clinic and phone visit as to their use of over the counter and prescription medications. The primary exclusion is prior use of any alpha-adrenergic receptor blocker for symptoms of CP/CPPS or for any other reason. During the course of the study, the participant MAY NOT initiate or otherwise consume any of the following medications:

- Tamsulosin hydrochloride (Flomax®)
- Terazosin HCL (Hytrin®)
- Doxazosin mesylate (Cardura®)

- Potent CYP3A4 inhibitors (i.e. ketoconazole, itraconazole, ritonavir)
- Erythromycin

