2 STUDY DESIGN AND OBJECTIVES

2.1 Primary Objectives

[figure not shown]
- 1. To compare 12 weeks of treatment with alfuzosin versus placebo in newly-diagnosed, alpha-blocker naïve CP/CPPS participants with respect to the primary endpoint in the NIH-CPSI.
- 2. To evaluate the safety and tolerability of 12 weeks of alfuzosin in newly-diagnosed, alpha-blocker naïve CP/CPPS participants.

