2.4 Study Time Frame

Approximately 270 eligible patients, 135 per treatment arm, will be randomized either to alfuzosin or to its matching placebo, and followed for a period of 12 weeks after randomization. There will be four (4) research clinic visits: Visit 1 (screening), Visit 2 (baseline/randomization), Visit 3 (6-week evaluation) and Visit 4 (12-week primary endpoint evaluation).

It is expected that the limitations of the inclusion criteria (recent onset and alpha-blocker treatment naive) may have an impact on the ability of the participating clinical centers to recruit these study participants. Each of the eleven (11) Clinical Sites (see next section) will randomize approximately 25 participants at the rate of one participant per month. Allowing for an additional twelve (12) weeks of follow-up on all participants, the total time required for accrual and follow-up for this trial is expected to be 28 months.

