Alfuzosin is a newer alpha-adrenergic blocking agent, which has been developed, tested, and used in Europe extensively for the treatment of benign prostatic hyperplasia (BPH). It is a quinazoline derivative (R,S)-N-[3-[(4-amino-6,7-dimethoxy-2-quinazolinyl) methylamino] propyl] tetrahydro-2-furancarboxamide hydrochloride, unlike tamsulosin hydrochloride (FLOMAX®) which is a methoxybenzene sulfonamide. Since it is an alpha-1 selective antagonist, dose titration is not necessary. Treatment-associated blood pressure alterations are small, although vasodilatory related adverse events may occur more frequently with alfuzosin than with placebo, suggesting that participants with symptomatic hypotension should be monitored closely. As with all alpha-blockers, there is the potential for syncope. Little or no incidence of abnormal ejaculation relative to placebo has been reported when participants use alfuzosin, 31;32 differing from those reported using other alpha-blockers. In clinical trials in the treatment of BPH, efficacy as measured by improvement in voiding symptoms and peak flow rates has been reported as significant compared to placebo.

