5.3.1 Risks of Alfuzosin (Uroxatral[®])

Alfuzosin is a synthetic antagonist of the alpha1 adrenergic receptor in humans. Hypersensitivity to alfuzosin can occur resulting in skin rashes, pruritis, urticaria, or angioedema. Participants with a known hypersensitivity to alfuzosin or any component of the drug formulation should be excluded. The principal risk of alpha-adrenergic blockers is a lowering of blood pressure while on the drug. This can result in dizziness, syncope, or postural hypotension. In the U.S studies of alfuzosin, symptomatic postural hypotension occurred in 2 of 473 men receiving 10 mg/day (0.4%) compared to none of 493 men receiving placebo. Participants should be warned of the risk of dizziness, lightheadedness, or syncope when taking alfuzosin. Alfuzosin should not be taken by men with moderate to severe hepatic impairment or co-administered with potent inhibitors of CYP3A4. Cimetidine can increase the level of alfuzosin. Alfuzosin should not be combined with antihypertensive medications. Individuals with congenital QT interval prolongation or patients with symptomatic angina pectoris should be monitored closely. Some tiredness, abdominal pain, dyspepsia, constipation, and nausea have been reported by men taking alfuzosin. Additional adverse events (between 1%-2% of patients receiving alfuzosin) include bronchitis, sinusitis, pharyngitis, tachycardia, and chest pain. In rare cases, alfuzosin has been associated with priapism and impotence.

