6.2.2 Warnings

Postural hypotension with or without symptoms (i.e. dizziness) may develop within a few hours following administration of alfuzosin. As with other alpha-adrenergic receptor blockers, there is a potential for syncope. Patients should be warned of the possible occurrence of such events when beginning alfuzosin and should avoid situations (ie. driving, operating machinery, or performing hazardous tasks) where injury could result should syncope occur during this period. Care should be taken when afuzosin is administered to patients who have had a hypotensive response to other medications.

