7.2 Screening Visit #1 (First Baseline Screening Visit)

The first screening visit should occur no more than four (4) weeks and no less than two (2) days

prior (when 2-day urine culture results are available) to randomization. During this screening visit, the forms and procedures listed below will be completed. If a participant fails to meet any of the study eligibility criteria, based on the data collected during this visit, he would not be required to complete the physical examination, urinalysis, or urine culture for the purposes of the study.

Eligibility Criteria. Each participant will complete a preliminary screening form that checks whether he meets the initial inclusion/exclusion/deferral criteria. These criteria will be verified at the second baseline visit.

Participant Contact Information. Participants will be asked to provide the clinical center with their address, phone (home, work, and cell) number, e-mail address, primary care physician, and the name, telephone number, and address of two other contacts. This information will be stored at the Clinical Center and available only to selected study personnel.

Participant Medical History. Each participant will provide the research staff with general medical history and specific genitourinary medical history. In particular, the participant will be asked to provide information regarding his disease and surgical histories.

Demographic Questionnaire. Each participant will provide the research staff with his demographic information, including date of birth (age), race, ethnicity, marital status, income, and level of education.

Participant Symptom Index. Each participant will provide the research staff with an assessment of his discomfort/pain by completing the NIH-CPSI and also complete the three questions about pain, urgency, and frequency on the SYM form.

Physical Examination. Each participant will undergo a focused physical examination at this baseline visit. This examination will include an abdominal exam, external genital exam, rectal exam, prostate exam, and perineal exam. If the participant has received a prior focused physical examination conducted by the Principal Investigator or his/her designee within four (4) weeks of study enrollment, a documented copy of this prior physical examination will be acceptable.

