Signs and Symptoms of Orthostasis in Clinical Studies: The adverse events related to orthostasis that occurred in the double-blind phase 3 studies with alfuzosin 10 mg are summarized in Table 2. Approximately 20% to 30% of patients in these studies were taking antihypertensive medication.

Table 2 — Number (%) of Patients with Symptoms Possibly Associated with Orthostasis in 3-Month Placebo-Controlled Clinical Studies

	Placebo	UROXATRAL
Symptoms	(n=678)	(n=473)
Dizziness	19 (2.8%)	27 (5.7%)
Hypotension or postural hypotension	0	2 (0.4%)
Syncope	0	1 (0.2%)

Multiple testing for blood pressure changes or orthostatic hypotension was conducted in the three controlled studies at each scheduled clinic visit (Days 14, 28, 56, and 84). Patients with a decrease in systolic blood pressure of \geq 20 mm Hg after 2 minutes standing following being supine were excluded from the three trials. These tests were considered positive for blood pressure decrease if (1) supine systolic blood pressure was \leq 90 mm Hg, with a decrease \geq 20 mm Hg versus baseline, and/or (2) supine diastolic blood pressure was \leq 50 mm Hg, with a decrease \geq 15 mm Hg versus baseline. The tests were considered positive for orthostatic hypotension if there was a decrease in systolic blood pressure of \geq 20 mm Hg upon standing from the supine position during the orthostatic tests. According to these definitions, decreased systolic blood pressure was observed in none of the 674 placebo patients and 1 (0.2%) of the 469 UROXATRAL® patients. Decreased diastolic blood pressure was observed in 3 (0.4%) of the placebo patients and in 4 (0.9%) of the UROXATRAL® patients. A positive orthostatic test was seen in 52 (7.7%) of placebo patients and in 31 (6.6%) of the UROXATRAL® patients.

A subset of 35 UROXATRAL[®] treated patients in study 1 had blood pressure measurements 12 to 16 hours after first dose administration to assess the potential to produce orthostatic hypotension. None of these patients showed a positive test for systolic, diastolic or orthostatic blood pressure change.

OVERDOSAGE

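### Safety is a primary objective and lowered blood pressure the named principal risk, but the protocol specifies no blood-pressure measurement, and section 6.2.1 refers to phone visits that are not in the schedule.

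*Protocol*

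**What the plan says.** Section 2.1 gives the second primary objective: "To evaluate the safety and tolerability of 12 weeks of alfuzosin in newly-diagnosed, alpha-blocker naïve CP/CPPS participants". Section 5.3.1 states the main hazard: "The principal risk of alpha-adrenergic blockers is a lowering of blood pressure while on the drug". Section 6.2.2 adds timing and form: "Postural hypotension with or without symptoms (i.e. dizziness) may develop within a few hours following administration of alfuzosin". Section 3.1 says that "participants with symptomatic hypotension should be monitored closely".

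The assessments are as follows:

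- **Visits.** Section 2.4: "There will be four (4) research clinic visits". These are screening, randomization, week 6 and week 12. Section 7.4 lists only weeks 6 and 12 after randomization, and Appendix A labels all four visits as clinic visits.
- **Examination.** Section 7.2 provides for one, at Screening Visit 1 (or a documented one from the preceding four weeks): "This examination will include an abdominal exam, external genital exam, rectal exam, prostate exam, and perineal exam".
- **Weeks 6 and 12.** Section 7.4 lists concomitant medications, adverse events and questionnaires, plus stop forms at week 12. Appendix A also has drug compliance, but no vital-signs form, and marks the physical examination at Visit 1 only.
- **Medication monitoring.** Section 6.2.1: "Participants will be monitored at each clinic and phone visit as to their use of over the counter and prescription medications".

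**The concern.** There are two separate problems.

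The first is a mismatch between an objective and its measurements. The protocol names a physiological effect as the principal risk and says it can occur without symptoms, but plans no reading that would show it. Section 8.1 counts abnormalities found on physical examination as adverse events, yet no examination is scheduled after randomization. If few hypotension events are reported, the final report could present this as reassurance under a primary objective, with no blood-pressure data behind it.

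The second is a contradiction. Section 6.2.1 relies on phone visits that nothing else in the protocol defines. If they were intended, their timing and content are missing. If not, the sentence is wrong. Sites cannot tell which.

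**Working it through.** **1. Search of the schedule.** Blood pressure appears in the background, risk, warning and side-effect text and in the product information of Appendix C. It does not appear in sections 2.4 or 7.1 to 7.4, or in the Appendix A grid. Count of specified blood-pressure measurements: 0. Count of scheduled phone visits: 0. First scheduled contact after dosing starts: 6 × 7 = day 42 of 12 × 7 = 84, which is halfway through treatment.

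**2. The protocol's own rates.** Section 5.3.1 and Appendix C give 2 of 473 men on alfuzosin 10 mg with hypotension or postural hypotension; Appendix C gives the other counts. For the orthostatic test I take the denominators 469 and 674 from the same paragraph of Appendix C. The stated percentages reproduce:

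- hypotension or postural hypotension, alfuzosin: 2/473 = 0.42% (stated 0.4%)
- syncope, alfuzosin: 1/473 = 0.21% (stated 0.2%)
- dizziness: 27/473 = 5.71% on alfuzosin, 19/678 = 2.80% on placebo (stated 5.7% and 2.8%)
- positive orthostatic test: 31/469 = 6.61% on alfuzosin, 52/674 = 7.72% on placebo (stated 6.6% and 7.7%)

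**3. What an arm of 135 would show.** Expected count = 135 × p; chance of at least one = 1 − (1 − p)^135.

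- Hypotension reports: 135 × 2/473 = 0.57; chance of any 43.6%.
- Syncope: 135 × 1/473 = 0.29; chance of any 24.9%.
- Dizziness: 135 × 27/473 = 7.7, against 135 × 19/678 = 3.8 at the placebo rate.

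The rates come from trials in men with benign prostatic hyperplasia, so carrying them over is an assumption. If the hypotension rate were half (1/473), 0.29 reports would be expected, with a 24.9% chance of any. If it were double (4/473), 135 × 4/473 = 1.14, with a 68% chance of any. Across that range, a count of zero or one is unsurprising whatever happens to measured blood pressure.

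**4. What measurement showed in the earlier trials.** Appendix C reports that blood pressure was tested at each scheduled visit (Days 14, 28, 56 and 84), and: "A positive orthostatic test was seen in 52 (7.7%) of placebo patients and in 31 (6.6%) of the UROXATRAL® patients". Per 135 men this is 135 × 31/469 = 8.9 on alfuzosin and 135 × 52/674 = 10.4 on placebo, a difference of about −1.5. Those trials could make that comparison because they measured both arms. This trial, as scheduled, could not.

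**The case against.** The strongest reply is that the safety objective is served by other means. Section 6.2 tells participants to report hypotension-type events immediately. Adverse events are recorded at randomization, week 6 and week 12, and whenever participants report them (section 8.1). Syncope is a serious adverse event by convention (section 8.2.1), reportable within 24 hours (section 8.2.2). Section 10.6 compares toxicity by body system and arm and sends safety analyses to the DSMB every six months. Section 3.1 calls treatment-related blood-pressure changes small. In Appendix C, none of 35 men measured 12 to 16 hours after the first dose had a positive test. Objective 2 names no blood-pressure endpoint. Medication use is recorded at all four clinic visits, so the phone reference may be a stray word.

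Most of this stands. It shows that symptomatic harm is captured and can be compared with placebo. It does not show that measured or asymptomatic change is captured. Nor does it remove the contradiction in section 6.2.1.

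A reader might go further and divide the 8.9 expected positive orthostatic tests by the 0.57 expected hypotension reports, concluding that symptom reporting misses about 15 events for each one it finds. The documents do not support that. Positive tests were no more frequent on alfuzosin (6.6%) than on placebo (7.7%), so the 8.9 is background and not missed drug harm. The ratio also leaves out dizziness, which did differ between arms (5.7% against 2.8%) and would be reported here.

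**Conclusion.** The point holds in a limited form. The protocol specifies no blood-pressure measurement, although it makes safety a primary objective and names lowered blood pressure as the principal risk. The information lost is asymptomatic or measured blood-pressure change. Symptomatic dizziness, hypotension and syncope are not lost. With about 0.57 hypotension reports expected among 135 men and a 44% chance of any, a near-zero count would say little about measured blood pressure. That figure assumes the Appendix C rate applies to this population.

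Three stronger readings are not supported:

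- That the trial cannot address objective 2 at all: reported events address much of it.
- That blood pressure will never be taken: the content of the examination form and the Manual of Procedures is not shown, so one can say only that the protocol specifies no reading.
- That nobody hears from participants before week 6: week 6 is the first scheduled contact, and participants are told to report events sooner.

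The phone-visit reference is a plain inconsistency. Its practical effect is limited, because medication use is recorded at every clinic visit.

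**What to change.** 1. Reconcile section 6.2.1 with section 2.4, section 7 and Appendix A on whether phone visits exist. If they do, the schedule must define them; if not, the reference should go. No contact schedule is proposed here.
2. Record blood pressure in both arms at clinic visits that already exist, before and during treatment, so that the arms can be compared. This costs one reading per visit and a field on a form. Such readings would not detect transient hypotension soon after the first doses, and a single reading does not replace the supine-to-standing test used in the earlier trials.
3. If readings are not added, restate objective 2 as participant-reported safety and tolerability, and draw no conclusion on measured blood pressure. This costs wording only.

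No clinical rule for acting on a reading is proposed.

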6.2.2 Warnings

Postural hypotension with or without symptoms (i.e. dizziness) may develop within a few hours following administration of alfuzosin. As with other alpha-adrenergic receptor blockers, there is a potential for syncope. Patients should be warned of the possible occurrence of such events when beginning alfuzosin and should avoid situations (ie. driving, operating machinery, or performing hazardous tasks) where injury could result should syncope occur during this period. Care should be taken when afuzosin is administered to patients who have had a hypotensive response to other medications.

6.2.3 Cautions

- The pharmacokinetics of alfuzosin have not been studied in patients with mild hepatic insufficiency.
- Caution should be exercised when alfuzosin is administered in patients with severe renal insufficiency.
- Use of alfuzosin should also be discontinued if symptoms of angina pectoris newly appear or worsen.

6.2.4 Contraindications

Alfuzosin should not be given to patients with moderate or severe hepatic insufficiency because the alfuzosin clearance rate is reduced in these individuals, resulting in a three- to four-fold higher alfuzosin plasma concentration compared to healthy subjects.

7 TRIAL TESTS AND PROCEDURES

7.1 Procedural Summary

Prior to the baseline screening, potential participants must have had symptoms of discomfort or pain in the pelvic region for at least a six-week interval at the time of presentation. Every potential study participant will undergo a series of screening procedures that take approximately 2 - 3 weeks to complete. The screening phase entails at least two clinic visits. The data collected and diagnostic procedures completed during this phase are identified in Sections 7.2 and 7.3, in the order in which they will be obtained or undergone. The order of the procedures has been selected to ensure that eligibility criteria checked by non-invasive methods precede those checked by more invasive methods, and to provide a balance of participant comfort and timeliness.

This study is comprised of phases for each participant: i) the screening phase and ii) the treatment and follow-up phase. The screening phase, which assesses a participant's eligibility via inclusion, exclusion, and deferral criteria, will consist of two baseline visits no more than four (4) weeks and no less than two (2) days apart (when 2-day urine culture results are available). Any candidate failing any of the inclusion or exclusion criteria, during either of the screening visits will be considered ineligible for the protocol. Some participants may have their entry into the study deferred to a later time based on the results of the deferral criteria.

7.2 Screening Visit #1 (First Baseline Screening Visit)

The first screening visit should occur no more than four (4) weeks and no less than two (2) days

prior (when 2-day urine culture results are available) to randomization. During this screening visit, the forms and procedures listed below will be completed. If a participant fails to meet any of the study eligibility criteria, based on the data collected during this visit, he would not be required to complete the physical examination, urinalysis, or urine culture for the purposes of the study.

Eligibility Criteria. Each participant will complete a preliminary screening form that checks whether he meets the initial inclusion/exclusion/deferral criteria. These criteria will be verified at the second baseline visit.

Participant Contact Information. Participants will be asked to provide the clinical center with their address, phone (home, work, and cell) number, e-mail address, primary care physician, and the name, telephone number, and address of two other contacts. This information will be stored at the Clinical Center and available only to selected study personnel.

Participant Medical History. Each participant will provide the research staff with general medical history and specific genitourinary medical history. In particular, the participant will be asked to provide information regarding his disease and surgical histories.

Demographic Questionnaire. Each participant will provide the research staff with his demographic information, including date of birth (age), race, ethnicity, marital status, income, and level of education.

Participant Symptom Index. Each participant will provide the research staff with an assessment of his discomfort/pain by completing the NIH-CPSI and also complete the three questions about pain, urgency, and frequency on the SYM form.

Physical Examination. Each participant will undergo a focused physical examination at this baseline visit. This examination will include an abdominal exam, external genital exam, rectal exam, prostate exam, and perineal exam. If the participant has received a prior focused physical examination conducted by the Principal Investigator or his/her designee within four (4) weeks of study enrollment, a documented copy of this prior physical examination will be acceptable.

Urinalysis, Urine, and EPS Specimens for Microscopy and Culture. Each participant will provide a VB2 specimen, a VB3 and/or EPS (expressed prostatic secretion) specimen for either analysis or culture. If the participant has provided these specimens as part of the focused physical examination conducted by the Principal Investigator or his/her designee within four (4) weeks of study enrollment, a documented copy of these laboratory results will be acceptable. The urine specimens will be collected via a modified "four-glass test" (FGT) described in Meares and Stamey³⁷. This FGT will be attempted one time only at Screening Visit #1 (at baseline).

Dipstick urinalysis will be conducted on the midstream urine (VB2) for macroscopic analysis. The VB2 specimen will also be cultured for 2 days to determine whether there is evidence of bacterial infection (UTI status). A positive culture will be defined as 1000 CFU/ml of urine and be the basis for participant exclusion in the trial. Both EPS and the post-EPS urine (VB3) will be collected and a microscopic urinalysis completed to quantify white blood cells. None of these samples will be banked under this protocol.

Next Visit Preparation.

• Appointment scheduling. An appointment will be made for Screening Visit #2, to occur no sooner than one (1) week and no later than four (4) weeks after Screening Visit #1.

• Concomitant medications. Each participant will receive instructions from the RC to bring to Screening Visit #2 all/or a list of all the over-the-counter and prescribed medications that he is currently taking.

